1. VERSION HISTORY

Table 1. Summary of Changes

Version/ Date	Associated Protocol Amendment	Rationale	Specific Changes
1 / 08 Sep 2022	Original 19 Jul 2022	N/A	N/A

2. INTRODUCTION

Nirmatrelvir a potent and selective inhibitor of the SARS-CoV-2 M^{pro} is being developed as an oral treatment of COVID-19. Ritonavir is a strong CYP3A4 inhibitor being used to inhibit the metabolism of nirmatrelvir in order to increase plasma concentrations of nirmatrelvir to values that are sufficient to suppress viral replication through the entire dosing interval.

The purpose of this study is to estimate the rBA of nirmatrelvir/ritonavir oral powder in 3 different food vehicles relative to the Paxlovid® tablets under fasted condition, and to estimate the effect of food on the rBA of the nirmatrelvir/ritonavir oral powder formulation in healthy adult participants. The study will also assess the safety, tolerability, and palatability of nirmatrelvir/ritonavir oral powder in healthy adult participants.

This SAP provides the detailed methodology for summary and statistical analyses of the data collected in Study C4671036.

2.1. Modifications to the Analysis Plan Described in the Protocol

None.

2.2. Study Objectives and Endpoints

Objectives	Endpoints
Primary:	Primary:

 To estimate the rBA of the nirmatrelvir/ritonavir [REDACTED] oral powder mixed with water compared to the nirmatrelvir/ritonavir [REDACTED] [REDACTED] commercial tablets under fasted conditions. 	
 The test/reference ratios for AUC_{inf} (if data permits), AUC_{last}, and C_{max} of nirmatrelvir and ritonavir.

Objectives	Endpoints

 • To estimate the rBA of the nirmatrelvir/ritonavir [REDACTED] oral powder mixed with infant formula compared to the nirmatrelvir/ritonavir [REDACTED] commercial tablets under fasted conditions. • To estimate the rBA of the nirmatrelvir/ritonavir [REDACTED] oral powder mixed with vanilla pudding compared to the nirmatrelvir/ritonavir [REDACTED] commercial tablets under fasted conditions. • To estimate the rBA of the nirmatrelvir/ritonavir [REDACTED] oral powder mixed with vanilla pudding under fed conditions compared to the nirmatrelvir/ritonavir [REDACTED] commercial tablets under fasted conditions. 	
Secondary:	Secondary:

 • To estimate the effect of food on the rBA of the nirmatrelvir/ritonavir [REDACTED] oral powder mixed with vanilla pudding. • To evaluate the safety and tolerability of nirmatrelvir/ritonavir in healthy participants. • To assess the palatability of nirmatrelvir/ritonavir oral powder mixed with water/ infant formula/ vanilla pudding. 	
 • The test/reference ratios for AUC_{inf} (if data permits), AUC_{last}, and C_{max} of nirmatrelvir and ritonavir. • Assessment of TEAEs, clinical laboratory abnormalities, vital signs, PEs, and 12 lead ECGs. • Assessment of palatability via questionnaire: mouth feel, bitterness, tongue/mouth burn, throat burn and overall liking.
[REDACTED]	[REDACTED]
[REDACTED]	[REDACTED]

Objectives	Endpoints
CCI [REDACTED]	[REDACTED]

2.3. Study Design

This is a Phase 1, open-label, single dose, randomized, crossover study in healthy adult participants to estimate rBA of nirmatrelvir/ritonavir CCI oral powder mixed with 3 different food vehicles (Test formulations) compared to the nirmatrelvir/ritonavir CCI [REDACTED] commercial tablets (Reference formulation) under fasted conditions, and to estimate the effect of food on the rBA of the nirmatrelvir/ritonavir oral powder formulation mixed with vanilla pudding. The study will also assess the safety, tolerability, and palatability of nirmatrelvir/ritonavir in healthy adult participants.

Approximately 12 adult healthy male and/or female participants will be enrolled and randomized to 1 of 6 possible treatment sequences. Participants who discontinue from the study for non safety reasons may be replaced at the sponsor's discretion in collaboration with the investigator. The replacement participant will receive the same treatment sequence as the participant who discontinued.

Each enrolled participant will participate in 5 study periods to receive 5 different treatments according to the sequence determined by randomization:

- Treatment A: Single oral dose of nirmatrelvir/ritonavir CCI tablets under fasted condition
- Treatment B: Single oral dose of nirmatrelvir/ritonavir CCI oral powder mixed in water under fasted condition
- Treatment C: Single oral dose of nirmatrelvir/ritonavir CCI oral powder mixed in infant formula under fasted condition
- Treatment D: Single oral dose of nirmatrelvir/ritonavir CCI oral powder mixed in vanilla pudding under fasted condition
- Treatment E: Single oral dose of nirmatrelvir/ritonavir CCI oral powder mixed in vanilla pudding under fed condition

Participants will be randomly assigned to 1 of 6 sequences as shown below in Table 2. Participants will be discharged on Day 4 of Period 5, following completion of all assessments. Between each treatment, a minimum of 4 days washout is proposed to minimize any residual nirmatrelvir concentrations prior to start of the next treatment. The total

planned duration of participation from the Screening visit to the last follow-up phone call, is approximately 12 weeks.

Table 2. Randomized Treatment Sequences

Treatment Sequence	Period 1	Period 2	Period 3	Period 4	Period 5
Sequence 1 (n=2)	Treatment A	Treatment B	Treatment C	Treatment D	Treatment E
Sequence 2 (n=2)	Treatment B	Treatment C	Treatment A	Treatment D	Treatment E
Sequence 3 (n=2)	Treatment C	Treatment A	Treatment B	Treatment D	Treatment E
Sequence 4 (n=2)	Treatment A	Treatment C	Treatment B	Treatment E	Treatment D
Sequence 5 (n=2)	Treatment B	Treatment A	Treatment C	Treatment E	Treatment D
Sequence 6 (n=2)	Treatment C	Treatment B	Treatment A	Treatment E	Treatment D

3. ENDPOINTS AND BASELINE VARIABLES: DEFINITIONS AND CONVENTIONS

3.1. Primary Endpoints

The primary endpoints are the test/reference ratios for AUC_{inf} (if data permits), AUC_{last} , and C_{max} of nirmatrelvir and ritonavir. Treatment A will be the Reference treatment while Treatments B, C, D, E will be the Test treatments.

[figure not shown]
3.2. Secondary Endpoints

The secondary endpoints are the following:

- The test/reference ratios for AUC_{inf} (if data permits), AUC_{last} , and C_{max} of nirmatrelvir and ritonavir, where Treatment D will be the Reference treatment while Treatment E will be the Test treatment.
- Safety and tolerability data, discussed in [Section 3.5](#).
- Palatability data, collected using the sponsor-provided questionnaire. The scores for each attribute (mouth feel, bitterness, tongue/mouth burn, throat burn, overall liking) will be derived by measuring the length (using a scale with gradations of at least 0.1 cm) of the “x” marked by the participant relative to the “good trait”.

CCI

Other exploratory endpoints include the test/reference ratios for AUC_{inf} (if data permits), AUC_{last} , and C_{max} of nirmatrelvir and ritonavir, where Treatment B will be the Reference treatment while Treatments C and D will be the Test treatments.

3.4. Baseline Variables

Baseline characteristics will be collected according to the schedule of activities (SoA) as specified in the protocol.

3.5. Safety Endpoints

The following data are considered in standard safety summaries (see protocol for collection days, baseline assessment, and list of parameters):

- adverse events (AE)
- laboratory data
- vital signs data
- electrocardiogram (ECG) results

3.5.1. Adverse Events

Any adverse events occurring following start of treatment will be considered as treatment emergent adverse event (TEAE). Events that occur during follow-up within the lag time of up to 28 days after the last of nirmatrelvir/ritonavir dose will be counted as treatment emergent and attributed to the last treatment taken. Events that occur during the washout period (up to 28 days from the last treatment) between study periods will be counted as treatment emergent and attributed to the previous treatment taken. The time period for collecting AEs (“active collection period”) for each participant begins from the time the participant provides informed consent.

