Physical Exam	X	X															
 • PE will be performed by trained medical personnel at the investigator site at Screening or Period 1 Day -1 only (height and weight must be obtained at Screening to obtain BMI for eligibility criteria). A brief PE may be performed at other designated time points at the discretion of the investigator.
Safety laboratory	X	X												X	X		
 • Safety laboratory assessments including urinalysis, hematology, and chemistry will be performed at Screening, Period 1 Day -1, Period 5 Day 4, and early termination/discontinuation if applicable. All the safety laboratory samples must be collected following at least a 4-hour fast. Additional safety laboratory assessments may be performed at any time at the discretion of the investigator.
FSH (postmenopausal women only)	X																
 • For confirmation of postmenopausal (amenorrheic for at least 12 consecutive months) female participants.
Urine drug testing	X	X															
 • Urine drug (mandatory) and alcohol breath test (at discretion of investigator) will be performed at Screening and on Period 1 Day -1. These tests may be performed at any other time at the discretion of the investigator.
Serology: HBsAg, HBsAb, HBcAb, HCVAb, and HIV	X																
 • HBsAb will be tested if HBsAg and/or HBcAb are positive.
Pregnancy test (WOCBP only)	X	X												X	X		

PFIZER CONFIDENTIAL

Table 1. Study Schedule of Assessment

Visit Identifier Abbreviations used in this table may be found in Appendix 10	Screening	Period 1				Period 2, 3 and 4				Period 5				F/U	E/T	Notes			
Days Relative to Day 1	Days -28 to -2	Day -1	1	2	3	4	1	2	3	4	1	2	3	4	28-35 Days				
Contraception check	X	X												X	X	X	
 • The investigator or his/her designee will discuss with the participant the need to use highly effective contraception consistently and correctly according to contraception guidelines (Appendix 4). 		
12-lead ECG (single)	X		X											X		X	
 • Single 12-lead ECG readings will be taken at specified time point. All ECG assessments will be made after at least a 5-minute rest in a supine position and prior to any blood draws or vital sign measurements. • The reading on Period 1 Day 1 will be done predose of Period 1 Day 1. 		

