Vital signs (BP/PR)	X		X				X				X			X		X	
 • Single supine BP and PR will be performed following at least a 5-minute rest in a supine position, at specified time point. BP, and PR assessments will be performed after collection of ECGs and prior to collection of blood draws if scheduled at the same time. Vital signs will be done predose, 2 hours and 6 hours post dose on Day 1 of each treatment period and also on Day 4 of Period 5. 		
COVID-19 questionnaire		X															
 • Check COVID-19 related signs and symptoms as per local procedures. 		
COVID-19 testing		X				X											
 • The testing for COVID-19 pathogen by RT-PCR will be performed as per local procedures. 		
Nirmatrelvir/ ritonavir dosing		X				X				X							
 • Nirmatrelvir/ritonavir will be administered orally after overnight fasting of 10 hours on Day 1 for treatments A, B, C and D and after high fat breakfast for treatment E. There will be at least a 4 day washout between each dose. 		

PFIZER CONFIDENTIAL

Table 1. Study Schedule of Assessment

Visit Identifier Abbreviations used in this table may be found in Appendix 10	Screening	Period 1				Period 2, 3 and 4				Period 5				F/U	E/T	Notes		
Days Relative to Day 1	Days -28 to -2	Day -1	1	2	3	4	1	2	3	4	1	2	3	4	28-35 Days		
 Screening will be performed within 28 days prior to the first dose of nirmatrelvir/ritonavir. Follow-up contact may occur via telephone contact and must occur 28 to 35 days from administration of the final dose of study intervention. 	
Palatability questionnaire Review			X				X										
 Review palatability questionnaire and instructions with participants prior to the first taste assessment to Treatment B, C and D on Day 1 of period 1 or 2. 	
Palatability Questionnaire			X				X				X						
 Each participant will record the sensory attributes at timed intervals of 1 (immediately after dosing), 5, 10 and 20 minutes after swallowing the suspension, using a Taste Assessment Questionnaire (see Appendix 9). PK assessments will take priority if the PK and palatability assessment conflict 	

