PK Blood Sampling for nirmatrelvir/ ritonavir		X	X	X	X	X	X	X	X	X	X	X	X	X			
 One (approximately 4 mL) blood sample for PK analysis of nirmatrelvir and ritonavir will be taken at the designated time points. See PK sampling schema in Table 2. 	
CCI				█											█			
CCI				█											█			
Serious and nonserious AE monitoring	X	→	→	→	→	→	→	→	→	→	→	→	→	X	X		
 See Section 8.4.3 for follow-up AE and SAE assessments. 	
Concomitant treatments	X	X	X	→	→	→	→	→	→	→	→	→	→	X	X	X	
 See Section 6.9 for additional information. 	

PFIZER CONFIDENTIAL

Table 1. Study Schedule of Assessment

Visit Identifier Abbreviations used in this table may be found in Appendix 10	Screening	Period 1				Period 2, 3 and 4				Period 5				F/U	E/T	Notes				
Days Relative to Day 1	Days -28 to -2	Day -1	1	2	3	4	1	2	3	4	1	2	3	4	28-35 Days		
 Screening will be performed within 28 days prior to the first dose of nirmatrelvir/ritonavir. Follow-up contact may occur via telephone contact and must occur 28 to 35 days from administration of the final dose of study intervention. 			
CRU discharge														X			
 Participants will be discharged from clinic on Day 4 of period 5 after collection of last PK sample. 			

Table 2. Pharmacokinetic Sampling Schema

Visit Identifier		Treatment Period 1 to 5														
Study Day		Day 1										Day 2	Day 3	Day 4		
Planned Hours Post Dose on That Day		0	0.5	1	1.5	2	2.5	3	4	6	8	12	16	24	48	72
PK blood sampling for nirmatrelvir/ritonavir		X	X	X	X	X	X	X	X	X	X	X	X	X	X	X

PFIZER CONFIDENTIAL

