4. STUDY DESIGN

4.1. Overall Design

This is a Phase 1, open-label, single dose, randomized, crossover study in healthy adult participants to estimate rBA of nirmatrelvir/ritonavir **CCI** [REDACTED] oral powder mixed with 3 different food vehicles (Test formulations) compared to the nirmatrelvir/ritonavir **CCI** [REDACTED] commercial tablets (Reference formulation) under fasted conditions, and to estimate the effect of food on the rBA of the nirmatrelvir/ritonavir oral powder formulation mixed with vanilla pudding. The study will also assess the safety, tolerability, and palatability of nirmatrelvir/ritonavir in healthy adult participants.

Approximately 12 adult healthy male and/or female participants will be enrolled and randomized to 1 of 6 possible treatment sequences. Participants who discontinue from the study for non safety reasons may be replaced at the sponsor's discretion in collaboration with the investigator. The replacement participant will receive the same treatment sequences as the participant who discontinued.

Each enrolled participant will participate in 5 study periods to receive 5 different treatments according to the sequence determined by randomization:

- Treatment A: Single oral dose of nirmatrelvir/ritonavir **CCI** [REDACTED] tablets under fasted condition
- Treatment B: Single oral dose of nirmatrelvir/ritonavir **CCI** [REDACTED] oral powder mixed in water under fasted condition
- Treatment C: Single oral dose of nirmatrelvir/ritonavir **CCI** [REDACTED] oral powder mixed in infant formula under fasted condition
- Treatment D: Single oral dose of nirmatrelvir/ritonavir **CCI** [REDACTED] oral powder mixed in vanilla pudding under fasted condition

- Treatment E: Single oral dose of nirmatrelvir/ritonavir **CCI** oral powder mixed in vanilla pudding under fed condition

Participants will be randomly assigned to 1 of 6 sequences as shown below in Table 3. Participants will be discharged on Day 4 of Period 5, following completion of all assessments. Between each treatment, a minimum of 4 days washout is proposed to minimize any residual nirmatrelvir concentrations prior to start of the next treatment. The total planned duration of participation from the Screening visit to the last follow-up phone call, is approximately 12 weeks.

Table 3. Randomized Treatment Sequences

Treatment Sequence	Period 1	Period 2	Period 3	Period 4	Period 5
Sequence 1 (N = 2)	Treatment A	Treatment B	Treatment C	Treatment D	Treatment E

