Sequence 2 (N = 2)	Treatment B	Treatment C	Treatment A	Treatment D	Treatment E
Sequence 3 (N = 2)	Treatment C	Treatment A	Treatment B	Treatment D	Treatment E
Sequence 4 (N = 2)	Treatment A	Treatment C	Treatment B	Treatment E	Treatment D
Sequence 5 (N = 2)	Treatment B	Treatment A	Treatment C	Treatment E	Treatment D
Sequence 6 (N = 2)	Treatment C	Treatment B	Treatment A	Treatment E	Treatment D

Healthy participants will be screened to determine eligibility within 28 days prior to study treatment. Medical history and results of PE, vital signs, 12-lead ECG, and clinical laboratory evaluations will determine eligibility. Eligible participants will be admitted to the CRU on Period 1 Day -1 and will be confined in the CRU until discharge which is Day 4 of Period 5.

On Day 1 of each period, participants will receive a single oral dose of study interventions nirmatrelvir/ritonavir **CCI** as per the randomization schedule. Study treatments A and D will be administered with approximately 240 mL of ambient temperature water and treatments B and C will be administered with approximately 210 mL of ambient temperature water under fasted conditions (10 hours overnight fast and no food until 4 hours after dosing). Study treatment E will be administered with approximately 240 mL of ambient temperature water approximately 30 minutes after the start of a standard high-fat, high-calorie breakfast. Serial PK samples will be collected up to 72 hours post dose. Participants will be discharged from the CRU on Period 5, Day 4 following completion of all assessments.

If a participant has any clinically significant, study related abnormalities at the conclusion of a scheduled inpatient portion of the study, the Pfizer medical monitor (or designated representative) should be notified and the participant may be asked to remain in the CRU until such abnormalities are deemed not clinically significant, or it is safe for outpatient follow-up.

A safety follow-up call will be made to participants approximately 28 to 35 days from administration of the final dose of study intervention.

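### The SAP's TEAE attribution rule gives Treatments D and E more attribution time than A, B and C, so any by-treatment TEAE summary would compare unequal windows: a minor point with a cheap fix

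*SAP*

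**What the plan says.** SAP 3.5.1 assigns treatment-emergent events to treatments in two steps. Events in follow-up, within 28 days of the final nirmatrelvir/ritonavir "dose will be counted as treatment emergent and attributed to the last treatment taken". Events in the washout between periods are "counted as treatment emergent and attributed to the previous treatment taken". The second rule also names 28 days as its limit, but the next dose ends that window first.

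The gap between doses has a stated minimum and no stated maximum. Protocol 1.3 reads: "There will be at least a 4 day washout between each dose".

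The sequence tables (Protocol 4.1, Table 3; SAP 2.3, Table 2) place A, B and C in Periods 1 to 3 and D and E in Periods 4 and 5 throughout. Sequences 1 to 3 end in E, and sequences 4 to 6 end in D.

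On observation, Protocol 4.1 says that participants "will be confined in the CRU until discharge which is Day 4 of Period 5". After that, one contact is planned: "A safety follow-up call will be made to participants approximately 28 to 35 days from administration of the final dose of study intervention".

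SAP 6.6.1 refers AE reporting to the sponsor's reporting standard (CaPS), which is not part of these documents. It states no common onset window, no exposure adjustment and no caveat about window length.

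**The concern.** In a crossover, a by-treatment AE table invites the reader to compare columns. That comparison is fair only if each treatment has a similar opportunity to have events counted against it. Here the opportunity depends on position in the sequence, and position is tied to treatment.

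Take an unrelated event on day 15 after a participant's last dose. It would be listed under D or E. With dose gaps of about a week or less, no completer could have an event that late listed under A, B or C, because another dose would have been given by then. Columns of 12 participants are small enough for one or two such events to show, and the natural comparison is powder in pudding (D, E) against tablets (A).

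What is at stake is limited. Safety and tolerability is a secondary objective, is not phrased by treatment, and is summarised descriptively.

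**Working it through.** The plan gives no figure for attribution time, so there is none to reproduce. The count below comes from the sequence table.

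**Inputs**
- 6 sequences with 2 participants each, 12 in all (Protocol 4.1, SAP 2.3); all are assumed to complete.
- Last treatment: E for 6 participants, D for 6.
- Window after the final dose: 28 days (SAP 3.5.1).
- Window after any earlier dose: the gap to the next dose, L days, with L at least 4 (Protocol 1.3).
- Discharge on Period 5 Day 4 after the last PK sample, taken as 3 days (72 h) after the final dose (Protocol 1.3, Tables 1 and 2).

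**Plausible gaps.** Protocol 4.1 gives the "planned duration of participation from the Screening visit to the last follow-up phone call, is approximately 12 weeks", or 84 days. Assume a full 28-day screening window and follow-up at 28 to 35 days. The total is then 28 + 4L + (28 to 35):
- L = 4: 72 to 79 days
- L = 5: 76 to 83 days
- L = 7: 84 to 91 days

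Gaps of about 4 to 7 days therefore fit the stated duration.

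**Attribution time**
- A, B and C are each followed by another dose in all 12 participants: 12 × L.
- D and E are each followed by another dose in 6 participants and are last in 6: 6 × L + 6 × 28.

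| Gap L | A, B, C (each) | D, E (each) | Ratio |
|---|---|---|---|
| 4 days | 12 × 4 = 48 | 24 + 168 = 192 | 4.0 |
| 5 days | 12 × 5 = 60 | 30 + 168 = 198 | 3.3 |
| 7 days | 12 × 7 = 84 | 42 + 168 = 210 | 2.5 |

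Equality needs 12L = 6L + 168, so L = 28 days. Four such gaps plus 28 days of follow-up come to 140 days before any screening, which the 12-week plan excludes.

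**Where the D and E time falls.** Days after discharge: 6 × (28 − 3) = 150 for each of D and E. The in-house remainder is 192 − 150 = 42 participant-days at 4-day gaps (A, B and C: 48) and 210 − 150 = 60 at 7-day gaps (A, B and C: 84). D and E thus have more attribution time in total but slightly to moderately less time under direct observation.

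**Early stopping.** A participant who stops after A, B or C gives that treatment the long window. One dropout after C in sequence 1 at 4-day gaps, not replaced, gives C 48 − 4 + 28 = 72, D 192 − 4 = 188 and E 192 − 28 = 164. The imbalance shifts but does not disappear.

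**Effect of a common 96 h window.** Every treatment has 12 × 4 = 48 participant-days. For D and E, 6 × 1 = 6 of these fall after discharge. Time leaving the A, B and C columns is 48 − 48 = 0 at 4-day gaps and 84 − 48 = 36 of 84 participant-days at 7-day gaps.

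**The case against.** The strongest reply is that no specified table is shown to be affected. SAP 6.6.1 leaves the AE tables to CaPS, which may already separate follow-up events. The only AE display it sets out by treatment is discontinuation due to AEs, and time after the fifth dose can hardly add to that. The rule is also coherent in itself: assigning an event to the most recent dose is a normal choice, 28 days matches the minimum active collection period in Protocol 8.4.1, and unequal realised time follows from short gaps. Nothing is tested, and the investigator assesses causality for each AE (Protocol Appendix 3).

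Most of this stands and sets the weight of the point. It does not remove the point: assigning events to treatments has little purpose unless they are shown by treatment, and nothing visible equalises the windows.

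A reader might infer from the ratios of 4.0 and 2.5 that D and E will show more adverse events than the tablets. The documents do not support that. They give no background AE rate for this setting and no basis for how completely one call captures events over 25 days at home, and in-house time is lower for D and E than for A, B and C.

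A reader might also blame this rule for two other imbalances. Routine safety laboratory tests "will be performed at Screening, Period 1 Day -1, Period 5 Day 4, and early termination/discontinuation if applicable", so for completers the only scheduled post-dose set falls after D or E, as does the only scheduled post-dose ECG. D and E also occupy only the last two periods. Both are features of the schedule and design; SAP 3.5.1 did not create them, and a common window would not cure them.

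**Conclusion.** The inequality is real and follows from the SAP's own rule and the sequence table. With 12 completers, D and E each have 192 participant-days against 48 for each of A, B and C at 4-day gaps, narrowing to 210 against 84 at 7-day gaps. The figures rest on full completion and, for the range of gaps, on reading the 12 weeks with a full screening window. They describe attribution time, not expected event counts.

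The consequence is confined to any descriptive by-treatment TEAE summary comparing D or E with A, B or C. D and E have equal time in total, so the food-effect pair is not disadvantaged, and the PK analyses do not use these data. The rule is not an error in TEAE definition and is suitable for overall reporting. This is an optional improvement.

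**What to change.** Add to SAP 3.5.1 or 6.6.1: in any by-treatment TEAE summary, events are counted by onset within one post-dose window that is the same for all five treatments and no longer than the minimum dose interval. A 96 h window would serve; a footnote should say that its last day after the Period 5 dose falls after discharge. Show later washout and follow-up events in a separate column. Flag events found by the Period 5 Day 4 procedures as such. Keep the 28-day rule for overall TEAE and SAE reporting.

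The cost is one SAP sentence, one table column and a footnote or flag. It needs no new data and no change to design or PK analysis. The downside is that later events leave the treatment columns. With 96 h this removes no A, B or C time at 4-day gaps, but at 7-day gaps it removes 36 of 84 participant-days for each of A, B and C, all of it in-house. The separate column keeps those events visible.
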